4. PARTICIPANT DISPOSITION

4.1. Participant Enrollment and Disposition

By-participant listings sorted by participant ID number (in ascending order) will be provided for the following:

- Enrollment
- Participant disposition, including cohort, date of enrollment, first dose date, last dose date, end of study date, study drug discontinuation, study discontinuation, and reasons for study drug or study discontinuation

4.2. Extent of Study Drug Exposure and Adherence

Total duration of exposure to study drug will be defined as last dosing date minus first dosing date plus 1, regardless of any temporary interruptions in study drug administration, and will be expressed in days. If the last study drug dosing date is missing, the last dosing date is imputed as the earliest date from the following:

- Day 5 if the participant took 2 tablets on Day 1
- Day 6 if the participant took 1 tablet on Day 1
- Last study visit date

Study day for the imputed last dosing date will not exceed Study Day 6.

A by-participant listing of study drug administration will be provided separately by participant ID number (in ascending order).

4.3. Protocol Deviations

Participants who did not meet the eligibility criteria for study entry but enrolled in the study, will be summarized regardless of whether they were exempted by the sponsor or not. A by-participant listing will be provided for those participants who did not meet at least 1 eligibility (inclusion or exclusion) criterion. The listing will present the eligibility criterion (or criteria if more than 1 deviation) that participants did not meet and related comments, if collected.

Protocol deviations occurring after participants entered the study are documented during routine monitoring. A by-participant listing will be provided for those participants with protocol deviations, included a column specifying whether the protocol deviation is important.

4.4. Assessment of Disaster or Public Health Emergency Impact

The study is in participants with COVID-19 thus no additional assessment of COVID-19 impact will be included.

5. BASELINE CHARACTERISTICS

5.1. Demographics and Baseline Characteristics

Demographics and baseline characteristics include:

- Age [in years]
- Age group (< 28 days; 28 days to < 2 years; 2 to < 12 years; 12 to < 18 years)
- Sex at birth (Male; Female)
- Race (American Indian or Alaska Native; Asian; Black; Native Hawaiian or Pacific Islander; White; Not Permitted; Other)
- Ethnicity (Hispanic or Latino; Not Hispanic or Latino; Not Permitted)
- Baseline body weight [in kg]
- Baseline body mass index (BMI) [in kg/m²]
- BMI-for-age Z-scores
- BMI-for-age percentile category (< 5th Percentile; 5th to < 85th Percentile; 85th to < 95th Percentile; ≥ 95th Percentile)
 - Details on BMI-for-age percentiles are available in [Appendix 2](#).

A by-participant demographic listing, including the informed consent date, will be provided by participant ID number (in ascending order). Note: If information on Apgar score for participants < 24 hours, head circumference (in cm) for participants < 28 days, birth weight (in kg) for participants < 56 days of age and/or gestational age (in weeks) for participants < 1 year has been collected this information will be listed.

5.2. Other Baseline Characteristics

Other baseline characteristics include:

- Duration of COVID-19 symptoms prior to first dosing date (days)
 - Defined as: First Dosing Date – Onset Date of First/Earliest COVID-19 Symptom
- Duration from first positive SARS-CoV-2 diagnostic test to first dosing date (days)
 - Defined as: First Dosing Date – Date of COVID-19 Diagnosis
- Risk factors linked to medical history:
 - **CCI**

- Total number of risk factors
- Baseline COVID-19 vaccination status: (a) Yes; (b) No
- Baseline respiratory viral coinfections: (a) None; (b) Yes subdivided into: (i) Influenza A; (ii) Influenza B; (iii) RSV
- Baseline SARS-CoV-2 viral load (as a continuous variable, and a categorical variable: (a) $< 6 \log_{10}$ copies/mL; (b) $\geq 6 \log_{10}$ copies/mL)
- Baseline eGFR using the bedside Schwartz formula (mL/min/1.73 m²)
- Baseline ALT (U/L)

A by-participant listing of other baseline characteristics will be provided by participant ID number (in ascending order).

5.3. Medical History

Medical history will be collected at screening for general conditions (ie, conditions not specific to the disease being studied). Medical history will be coded using the current Medical Dictionary for Regulatory Activities (MedDRA) dictionary.

General medical history data will be collected at screening and listed only.

6. EFFICACY ANALYSES

6.1. Primary Efficacy Endpoint

There is no primary efficacy endpoint in this study.

6.2. Secondary Efficacy Endpoints

By-participant listings sorted by participant ID number (in ascending order) will be provided for the following:

- COVID-19 symptoms assessed by the participant and/or caregiver COVID-19 symptom assessment questionnaire data
- SARS-CoV-2 nasal swab viral load
- Oxygen supplementation
- Hospitalization

CCD

[REDACTED]

[REDACTED]

[REDACTED]

6.4. Changes From Protocol-Specified Efficacy Analyses

The definition of the Virology Analysis Set was modified so that participants with a baseline SARS-CoV-2 viral load < LLOQ will not be included in the Virology Analysis Set.

This study was terminated early; hence the protocol-specified efficacy analyses will not be provided. Only by-participant listings will be presented.

7. SAFETY ANALYSES

7.1. Adverse Events and Deaths

7.1.1. Adverse Event Dictionary

Clinical and laboratory AEs will be coded using the current version of MedDRA. System organ class, high-level group term (HLGT), high-level term (HLT), preferred term, and lowest-level term (LLT) will be provided in the AE dataset.

7.1.2. Adverse Event Severity

The severity of AEs will be graded using the Division of AIDS (DAIDS) Table for Grading the Severity of Adult and Pediatric Adverse Events, Version 2.1 dated July 2017. For each episode, the highest grade attained should be reported as defined in the grading scale. The DAIDS scale is available at the following location:

<https://rsc.niaid.nih.gov/sites/default/files/daidsgradingcorrectedv21.pdf>

Adverse events are graded by the investigator as Grade 1, 2, 3, 4, or 5 (fatal) according to toxicity criteria specified in the protocol. The severity grade of events for which the investigator did not record severity will be categorized as “missing” for tabular summaries and data listings. The missing category will be listed last in summary presentation.

7.1.3. Relationship of Adverse Events to Study Drug

Related AEs are those for which the investigator selected “Related” on the AE eCRF to the question of “Related to Study Treatment.” Relatedness will always default to the investigator’s choice, not that of the medical monitor. Events for which the investigator did not record relationship to study drug will be considered related to study drug for summary purposes. However, by-participant data listings will show the relationship as missing.

7.1.4. Serious Adverse Events

Serious adverse events (SAEs) will be identified and captured as SAEs if the AEs met the definitions of SAEs that were specified in the study protocol. SAEs captured and stored in the clinical database will be reconciled with the SAE database from the Gilead Global Patient Safety Department before data finalization.

7.1.5. Treatment-Emergent Adverse Events

7.1.5.1. Definition of Treatment-Emergent Adverse Events

Treatment-emergent adverse events (TEAEs) are defined as 1 or both of the following:

- Any AEs with an onset date on or after the study drug start date and no later than 30 days after permanent discontinuation of study drug
- Any AEs leading to premature discontinuation of study drug.

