7.1.6. Summaries of Adverse Events and Deaths

7.1.6.1. Summaries of AE incidence in Combined Severity Grade Subsets

By-participant listings will be provided for the following:

- All AEs, indicating whether the event is treatment emergent
- All Deaths

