7.2.1.1. Treatment-Emergent Laboratory Abnormalities

Treatment-emergent laboratory abnormalities are defined as values that increase at least 1 toxicity grade from baseline at any postbaseline time point, up to and including the date of last dose of study drug plus 30 days participants who permanently discontinued study drug, or the last available date in the database snapshot for participants who were still on treatment at the time of an interim analysis. If the relevant baseline laboratory value is missing, any abnormality of at least Grade 1 observed within the time frame specified above will be considered treatment emergent.

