Appendix 1. Schedule of Assessments

	Screening/ (D -1) ^a	Baseline/ D 1 ^a	D 3	D 5	D 8	D 14	D 21	D 28	EOS/ D 35
	-	-	-	-	± 1 d	± 2 d	± 2 d	± 2 d	± 5 d
	In person		In person or remote ^b	In person	In person or remote ^b		Virtual ^c		In person
Participant and/or parent or legal guardian consent/assent									
Medical history ^d									
Document SARS-CoV-2 infection									
Complete physical examination ^e									
Symptom-directed physical examination ^e									
Body weight									
Height/length ^f									
Last recorded Apgar score if < 24 hours of age									
Birth weight if < 56 days of age									
Gestational age if < 1 years of age									
Vital signs ^g									
Tanner stage assessment if ≥ 6 years of age									
Hematology, chemistry									
Urinalysis									
Routine coagulation test (PT/aPTT with calculated INR)									
Neonatal bilirubin panel for all neonates < 14 days, and any neonate presenting with jaundice									
Urine pregnancy test ^h									
Midturbinate nasal swab ⁱ									
Review inclusion/exclusion criteria									
Participant and/or caregiver symptom assessment ^j									
PK sample ^k									
Study drug dispensation									
Study drug administration ^l									
Study drug return ^m									
Concomitant medications									
Hospitalization details ⁿ									
Oxygen supplementation requirement ^o									

CCI

	Screening/ (D -1) ^a	Baseline/ D 1 ^a	D 3	D 5	D 8	D 14	D 21	D 28	EOS/ D 35		
	-	-	-	-	± 1 d	± 2 d	± 2 d	± 2 d	± 5 d		
	In person		In person or remote ^b	In person	In person or remote ^b	Virtual ^c		In person			
Adverse events ^d	CCI										
Acceptability/palatability assessment											

aPTT = activated partial thromboplastin time; COVID-19 = coronavirus disease 2019; D/d = day; EOS = end of study; Ig = immunoglobulin; INR = international normalized ratio; MAP = mean arterial pressure; PT = prothrombin time; PK = pharmacokinetic(s); RT-qPCR = reverse transcription-quantitative polymerase chain reaction; SARS-CoV-2 = severe acute respiratory syndrome coronavirus 2

- a Screening window is within 48 hours of the baseline visit. Baseline visit may occur on the same day as screening. If the Day 1 and Screening visits occur within the same calendar day, do not repeat assessments common to Screening and Day 1 visits.
- b An in-person visit will occur either at a medical facility or as a remote visit at home by a health care professional (where permitted).

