Events with Missing Onset Day and/or Month

An event is considered TE if all of the following 3 criteria are met:

- a) The month and year (or year) of onset date is the same as or after the month and year (or year) of the first dose of study drug administration, and
- b) The month and year (or year) of the onset date is the same as or before the month and year (or year) of the 30th day after the date of the last dose of study drug administration, and
- c) End date is as follows:
 - i) The (complete) end date is on or after the first dose date, or
 - ii) The month and year (or year) of end date is the same as or after the month and year (or year) of the first dose of study drug, or
 - iii) End date is completely missing

Events with Completely Missing Onset Date

An AE with a completely missing onset date is defined as TEAE if end date meets any of the 3 criteria specified above.

- 10) The precision in reporting numerical values should be as follows:
 - a) Raw measurements will be reported the same as the data captured electronically or on the eCRF for all but hematology and chemistry values.
 - b) SD and SE will be reported to one more significant decimal place than the raw measurement.
 - c) Mean, median, minimum, Q1, Q3, and maximum will be reported to the same number of decimal places of the raw measurements.

Exceptions may be considered; for eg, if more than 4 significant digits are provided for the measurement.

Precision for derived parameters as follows:

Parameters	Decimal Places
BMI	2
PK concentration	2

- 11) Incomplete death dates will be imputed as the maximum of the study drug start dates, study drug end dates, clinic or virtual visit dates (LSTSVDT), laboratory visit dates (LSTLBDT), COVID-19 symptom assessment questionnaire dates plus 1.

- 12) Graded Laboratory Abnormalities Summary

The following labels will be used for laboratory abnormalities listings:

Category	Lab Test Label Used in I-lbtox Listing	Toxicity Direction	Lab Test Label Used in t-lbtox Table
Hematology	Hemoglobin	Decrease	Hemoglobin (Decreased)
	Lymphocytes	Decrease	Lymphocytes (Decreased)
	Neutrophils	Decrease	Neutrophils (Decreased)
	Platelets	Decrease	Platelets (Decreased)
	WBC	Decrease	WBC (Decreased)
Chemistry	Albumin	Decrease	Albumin (Decreased)
	Alkaline Phosphatase	Increase	Alkaline Phosphatase (Increased)
	ALT	Increase	ALT (Increased)
	AST	Increase	AST (Increased)
	Bicarbonate	Decrease	Bicarbonate (Decreased)

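### The treatment-emergent AE definition has no worsening criterion, so an event that starts before first dose and rises in grade on drug can be listed at its peak grade and flagged not treatment-emergent

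*SAP*

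**What the plan says.** SAP Section 7.1.5.1 opens with "Treatment-emergent adverse events (TEAEs) are defined as 1 or both of the following" and gives two criteria. The first is "Any AEs with an onset date on or after the study drug start date", with an upper limit of 30 days after permanent discontinuation. The second is "Any AEs leading to premature discontinuation of study drug", which has no limit on onset date.

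On grading, Section 7.1.2 says "For each episode, the highest grade attained should be reported as defined in the grading scale".

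The incomplete-date rules (Section 7.1.5.2 and Appendix 2, item 9) compare partial onset dates with the month and year of first and last dose, and partial end dates with those of first dose. The Appendix 2 condition begins "The month and year (or year) of onset date is the same as or after". Neither place mentions a change in severity.

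For laboratory data, Section 7.2.1.1 defines treatment-emergent abnormalities as "values that increase at least 1 toxicity grade from baseline at any postbaseline time point", within the same 30-day limit.

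The AE output in Section 7.1.6.1 is a listing of "All AEs, indicating whether the event is treatment emergent", plus a listing of deaths. Section 3 states that the study will have no tables or figures. Footnote a of Appendix 1 sets the pre-dose period: "Screening window is within 48 hours of the baseline visit". It also allows both visits on the same day.

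**The concern.** Treatment-emergent AE incidence by Day 35 is one of the primary endpoints (Section 1.1). With tables withdrawn after early termination, the flag in the AE listing is the only AE read-out of that endpoint left. The flag depends on onset date, apart from the discontinuation route, while the listed grade is the peak of the episode. One line can therefore pair a pre-dose onset date and a not-emergent flag with a grade that was reached only on drug. A reader could take that grade as present before treatment.

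The gap runs one way: for the case at issue it can only withhold the flag. Elsewhere the SAP leans the other way. Section 7.1.5.2 treats an AE with both dates completely missing as emergent, and Section 7.1.3 counts missing relatedness as related for summary purposes.

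**Working it through.** The SAP gives no AE counts, so there is no figure to reproduce. The check applies the two criteria of Section 7.1.5.1, joined by 'or', to each combination of onset, worsening and discontinuation. Dates are taken as complete, and AEs are assumed to be recorded from screening.

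| Case | Onset date | Course | Flag under 7.1.5.1 | Route |
|---|---|---|---|---|
| A | On or after first-dose date, within the 30-day limit | Any | Emergent | Criterion 1 |
| B | First-dose date, but before the dose is taken | Any | Emergent | Criterion 1, because it compares dates and not times |
| C | Earlier calendar date | No worsening, drug not stopped for it | Not emergent | None |
| D | Earlier calendar date | Leads to premature discontinuation | Emergent | Criterion 2 |
| E | Earlier calendar date | Worsens on drug, drug not stopped for it, kept as one record | **Not emergent** | None |
| F | Earlier calendar date | Worsens on drug and is entered as a new AE with a new onset date | New record emergent | Criterion 1 |

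Only case E goes wrong. Under Section 7.1.2 its listed grade is the on-drug peak.

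*Comparison with the laboratory rule.* Take a hypothetical child with raised ALT reported as a Grade 1 AE the day before first dose, Grade 1 at baseline and Grade 3 on Day 3, with drug continued. The laboratory rise is 3 − 1 = 2 grades. This meets the threshold of at least 1, so the result is a treatment-emergent abnormality. The AE, kept as one record, has its onset on Study Day −1, before Study Day 1. It meets neither AE criterion and is flagged not emergent. Section 7.1.1 confirms that laboratory AEs are coded as AEs, so the same worsening can carry opposite labels in two listings.

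*Exposed window.* Screening falls within 48 hours of baseline. If AEs are recorded from screening, the onset must lie in at most about 48 hours and on a calendar date before first dose. The window is zero when screening and Day 1 share a date. An onset date missing only its day, in the same month and year as first dose, is treated as emergent if the end date also qualifies, so the exposure is mainly to complete dates.

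*Effect of a worsening criterion.* Case E becomes emergent. If the criterion also covers events that become serious, an event of type C that turns serious without a change of grade becomes emergent too. The remaining cases keep their flags.

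**The case against.** The strongest objection is that the fault depends on a recording rule that is not in the SAP. Section 7.1.2 asks for the highest grade per episode, but it neither defines an episode nor says whether a rise in grade starts a new record. That rule normally sits in the protocol or the eCRF instructions. If a worsened event is entered as a new AE, case F applies and the gap disappears. This stands, and it makes the point conditional.

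Second, nothing is lost from the report. Every AE is listed whatever its flag, and with few participants a reader can inspect each line. In the ALT example the rise also appears as a treatment-emergent laboratory abnormality, and Section 7.2.2 lists liver threshold cases separately. This stands too and limits the consequence to a wrong flag.

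Third, laboratory tests have a measured baseline grade and repeated values, whereas an AE episode carries one reported grade. Different rules need not contradict each other. That is fair: the laboratory rule shows that the SAP treats worsening as emergent in one place, not that the text is self-contradictory.

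Some stronger readings are tempting, and the SAP does not support them:

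- *The definition counts only events with onset on or after first dose.* The discontinuation criterion captures events of any onset date.
- *Every pre-dose event that worsens is misclassified.* The recording rule is not visible, and case D is captured.
- *One such event moves cohort incidence by at least 1/12, about 8 percentage points.* No incidence is tabulated. Incidence would count participants, so a child with another treatment-emergent AE would not change it. Twelve is the planned size of Cohorts 1–4 only.
- *Children who are symptomatic at entry enlarge the problem.* Footnote d of Appendix 1 places COVID-19 symptoms and other conditions in medical history. How worsening of those is recorded cannot be seen here.

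**Conclusion.** The point holds in a limited form. Section 7.1.5.1 has no worsening criterion and the incomplete-date rules add none. An AE that starts on a calendar date before first dose, rises in grade on drug, does not lead to discontinuation and stays in one record is listed at its on-drug peak and flagged not treatment-emergent. The laboratory rule in the same SAP would count a comparable rise.

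The consequence is a wrong flag on the remaining AE read-out of a primary safety endpoint. No event is lost and no summary figure changes. The number of affected events is unknown and may be zero.

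The conclusion rests on two assumptions: that a worsened event keeps its record and onset date, which Section 7.1.2 suggests without settling, and that AEs are recorded from screening. The gap is still worth closing, because the remedy is small and the records to check are few.

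**What to change.** Add a third criterion to Section 7.1.5.1: *any AE with onset before the study drug start date that increases in severity grade or becomes serious on or after that date, within the 30-day limit of the first criterion*. Carry it into item 9 of Appendix 2 so that the programmed flag follows the definition.

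If the date of grade change was not collected, review each AE that has pre-dose onset and was ongoing after first dose, before database finalization. Query where needed, and mark unresolved records in the listing as *worsening cannot be excluded*.

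If the eCRF rules already require a worsened event to be entered as a new AE, a sentence in Section 7.1.5.1 citing that rule is enough and no new criterion is needed.

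If the SAP is already final, Section 1 provides for documenting the change in the CSR.

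The cost is one sentence, one change to the flag derivation and possibly a few data queries. The downside is that the number of AEs flagged treatment-emergent may rise slightly.

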7.1.5.2. Incomplete Dates

If the onset date of the AE is incomplete and the AE stop date is not prior to the first dosing date of study drug, then the month and year (or year alone if month is not recorded) of onset determine whether an AE is treatment emergent. The event is considered treatment emergent if both of the following 2 criteria are met:

- The AE onset is the same as or after the month and year (or year) of the first dosing date of study drug, and
- The AE onset date is the same as or before the month and year (or year) of the date corresponding to 30 days after the date of the last dose of study drug

An AE with completely missing onset and stop dates, or with the onset date missing and a stop date later than the first dosing date of study drug, will be considered to be treatment emergent. In addition, an AE with the onset date missing and incomplete stop date with the same or later month and year (or year alone if month is not recorded) as the first dosing date of study drug will be considered treatment emergent.

7.1.6. Summaries of Adverse Events and Deaths

7.1.6.1. Summaries of AE incidence in Combined Severity Grade Subsets

By-participant listings will be provided for the following:

- All AEs, indicating whether the event is treatment emergent
- All Deaths

7.2. Laboratory Evaluations

Laboratory data collected during the study will be analyzed using both quantitative and qualitative methods. The analysis will be based on values reported in conventional units. When values are below the LOQ, they will be listed as such, and the closest imputed value will be used for the purpose of calculating summary statistics as specified in Section 3.7.

A by-participant listing for laboratory test results will be provided by participant ID number and visit in chronological order for hematology, serum chemistry, and coagulation separately. Values falling outside of the relevant reference range and/or having a severity grade of 1 or higher will be flagged in the data listings, as appropriate.

